## 10.1.14 End of Study (EOS) Visit

The EOS visit will occur after confirmed disease progression, or after withdrawal from the study for other reasons, or at a maximum of 3 years from the first study drug administration. The EOS visit will occur at least 28 days after last study drug administration but should be performed before any new MM therapy starts, whichever occurs first.

At the EOS visit, the following will be obtained, performed, or assessed:

- Toxicity/AE assessment since the last visit
- Concomitant medications
- Karnofsky performance status
- Blood sample for hematology, serum chemistry, coagulation, βHCG pregnancy test for women of childbearing potential, MOR03087 pharmacokinetics (only if subject had no follow-up visit), endocrinology, anti-MOR03087 antibodies, B, T, and NK cells, serum M-protein, and serum FLCs
- Urine sample for urinalysis
- Sample from 24-hour urine for urine M-protein
- Bone skeletal survey by x-ray, CT, or MRI imaging (where medically indicated, as a regular assessment of standard of care in subjects with relapsed or refractory MM)
- Response assessment
- Physical examination (including basic neurological examination of general motor and sensory systems, mental status, cranial nerves, and coordination)
- Ocular examination by an ophthalmologist (including distance visual acuity, optical coherence tomography [if available], and ophthalmoscopy under full mydriasis [if optical coherence tomography is unavailable])
- Body weight
- Quality of life questionnaires (QLQ-MY20 and QLQ-C30)
- 12-Lead ECG
- Vital signs (blood pressure, pulse rate, respiratory rate, and body temperature)
- Documentation of subject's subsequent anti-myeloma therapy, as appropriate

For subjects receiving POM or LEN, the additional following will be obtained, performed, or assessed:

• Clinical review of signs/symptoms for possible VTEs in subjects treated with POM or LEN. Subjects who develop symptomatic deep vein thrombosis will be assessed and diagnosed objectively by Doppler ultrasonography or a comparable method per institution's standard of care. See Appendix 18.9 for deep vein thrombosis and pulmonary embolism diagnostic algorithms

## 11 EFFICACY, PHARMACOKINETIC, SAFETY, AND OTHER VARIABLES

The endpoints to be assessed for this study are as follows:

#### **Primary Endpoints**

- 1. Determination of the MTD and/or recommended dose of MOR03087 as monotherapy, in combination with DEX, and in combination with POM+DEX and LEN+DEX
- 2. Determination of the recommended dosing regimen of MOR03087
- 3. Incidence and severity of adverse events (AEs)
- 4. Immunogenicity of MOR03087 based on both absolute (number and percentage of subjects who develop anti-MOR03087 antibodies) and semi-quantitative (anti-MOR03087 antibody titer determination of confirmed positive samples) assessments

### Secondary Endpoints

- 1. Pharmacokinetics of MOR03087 +/- LEN or POM
- 2. Absolute and percent change from baseline in measurements of B, T, and NK cell populations
- 3. Overall response rate (stringent complete response [sCR], complete response [CR], very good partial response [VGPR], partial response [PR]), further tumor response rates (CR, stringent complete response [sCR], PR, minimal response [MR], VGPR), and SD rate
- 4. Duration of response, time to progression (TTP), and PFS
- 5. Absolute and percentage change from baseline in serum and urine M-protein levels
- 6. Absolute and percent change from baseline in serum FLC levels and serum FLC ratio
- 7. Absolute changes from baseline in laboratory parameters (serum chemistry, hematology, urinalysis) and clinically relevant abnormal values
- 8. Absolute change from baseline in overall quality of life scores
- 9. Change in cytokines from baseline

## **11.1 Efficacy and Pharmacodynamic Assessments**

#### **11.1.1 Efficacy Assessment**

Efficacy will be evaluated in terms of overall response rate (ORR) (sCR + CR + VGPR + PR) (Kyle 2009), further tumor response rates (CR, sCR PR, MR, VGPR), SD rate, duration of response, TTP, and PFS, using the modified European Group for Blood and Marrow Transplantation (EBMT) criteria (Blade 1998) plus the International Myeloma Working Group Uniform Response Criteria (2006), taking the supplement by Kyle (Kyle 2009) into consideration.

All of these tumor response criteria for MM are defined in Appendix 18.3. All of them are based on the International Myeloma Working Group Uniform Response Criteria (Durie 2006 and

Erratum 2007), except for MR, which is based on the EBMT criteria (Blade 1998). Disease progression is defined as progressive disease according to the IMWG, 2006 (see Appendix 18.3, Table 14), death or start of new anti-MM treatment.

All responses need two consecutive assessments, ideally being confirmed at Day 1 of the next cycle.

The response evaluation will be based on serum and urine M-protein levels, serum FLC level, and FLC ratio.

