¹ A follow-up visit will be repeated every fourth week (± 2 days) until progressive disease, or receipt of new anti-myeloma treatment, or until death, but no longer than 3 years from the first study drug administration. Follow-up visits may be delayed for a maximum of 2 weeks after the normal visit window due to other reasons (e.g., logistical).

² The EOS visit will occur after at least 28 days after last study drug administration but should be performed before any new MM therapy starts, whichever occurs first. Subjects who complete Cycle 2 but do not receive additional cycles (Cycle 3+) have to perform Follow-up visit 1 and Follow-up visit 2 before EOS visit.

³ Including disease staging based on Durie-Salmon and International Staging System (ISS) criteria and documentation of immunoglobulin type.

⁴Before study drug administration.

⁵ Each cycle, starting with Cycle 3+: pre-dose at Day 1 (CxD1)

⁶ During Cycle 1, all subjects should be given premedication including an antipyretic (e.g., paracetamol) and a histamine H1 receptor blocker according to the local standard of care. In medically justified cases, the investigator may use other medications (e.g., steroids as per local standard but not exceeding 10 mg prednisolone equivalent), doses and/or formulations if this is documented thoroughly in the eCRF and the source data. If no infusion reaction occurs during Cycle 1, then premedication can be stopped at discretion of the investigator for subsequent treatment cycles. Otherwise, the premedication should be continued for subsequent administrations of MOR03087 as well.

⁷ Emergency Laboratory only to be taken if hematology/serum chemistry is not available prior to study drug administration

⁸ Sample to be taken and evaluated before study drug administration. On Day 1, additional sample (except AST and ALT) to be taken 2 hours after end of infusion.

⁹ β2-microglobulin to be measured at Screening only.

¹⁰ Pharmacokinetic sample to be taken predose and then at 1, 2, 4, 8, 14±2 (optional), 22±2, and 28±2 hours after start of first infusion.

¹¹ Pharmacokinetic sample to be taken predose and 2 hours after start of infusion.

¹² Pharmacokinetic sample during treatment Cycles 3+ to be taken every 2nd study drug administration (CxD15) predose and 2 hours after start of infusion.

¹³ Only if subject had no follow-up visit.

¹⁴ Samples for anti-MOR03087 antibodies will also be used to determine tetanus titer if sufficient quantities of serum are available.

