#### Follow-Up Visit 2 and Subsequent Follow-Up Visits:

Four weeks ( $\pm 2$  days) after Follow-up Visit 1, a second follow-up visit will occur. If there is still a response to therapy at this visit, then a follow-up visit will be repeated every fourth week ( $\pm 2$  days) until there is a disease progression (but no longer than 3 years), death, or the subject starts a new anti-myeloma therapy. Follow-up visits may be delayed for a maximum of 2 weeks after the normal visit window due to other reasons (e.g., logistical).

At each of these visits, the following will be obtained, performed, or assessed:

- Toxicity/AE assessment since the last visit
- Concomitant medication
- Karnofsky performance status
- Blood sample for hematology, serum chemistry, βHCG pregnancy test for women of childbearing potential, anti-MOR03087 antibodies (at Follow-up Visit 2 only), B, T, and NK cells, serum M-protein, and serum FLCs
- Sample from 24-hour urine for urine M-protein
- Response assessment, to be continued until disease progression or death or subsequent anti MM therapy start whatever occurs first. Note: all responses require two consecutive assessments, and should ideally be confirmed at the next follow-up visit.
- Physical examination (including basic neurological examination of general motor and sensory systems, mental status, cranial nerves, and coordination)
- Body weight
- Quality of life questionnaires (QLQ-MY20 and QLQ-C30)
- 12-Lead ECG, if clinically indicated at the discretion of the investigator
- Vital signs (blood pressure, pulse rate, respiratory rate, and body temperature)
- Clinical review of signs/symptoms for possible VTEs in subjects treated with POM or LEN. Subjects who develop symptomatic deep vein thrombosis will be assessed and diagnosed objectively by Doppler ultrasonography or a comparable method per institution's standard of care. See Appendix 18.9 for deep vein thrombosis and pulmonary embolism diagnostic algorithms

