7.3.3.3 Time-related efficacy endpoints

With respect to the time-related efficacy endpoints defined subsequently, a single PD assessment which did not cause a discontinuation of treatment and which has been disproven by the next consecutive non-missing tumor assessment will not be considered when determining the date of first progression and the censoring variables.

Thus, the date of progression used for the derivations will be the date of progression related to the first PD assessment that fulfills at least 1 of the following criteria:

- the next consecutive non-missing tumor assessment is also PD
- the PD assessment is the last tumor assessment in the study

The start date for sCR, CR, VGPR, PR, MR and SD is defined as the date of the first time point at which the response was noted, provided that the response was confirmed at a later time point (as described in section 7.3.3.2). However, a response followed by ≥ 2 non-confirming consecutive non-missing planned response assessments will not be considered for the determination of the first date at which the response was noted.

The date of death due to progression is the stop date of AEs with a fatal outcome and a preferred AE term “Disease progression” or “Multiple myeloma”.

All time-related efficacy endpoints defined below will be reported in months.

Secondary efficacy endpoint variables:

Duration of response (DoR): The duration of response will be calculated in the subgroup of subjects showing confirmed sCR, CR, VGPR or PR. Duration of response will be defined as the time from date of first response (sCR, CR, VGPR or PR) until date of progression or death due to progression (as defined above) whichever is documented first. For censoring rules see Table 2.

Time to progression (TTP): Time to progression will be defined as the time from Cycle 1, Day 1 until date of progression or death due to progression (as defined above) whichever is documented first. For censoring rules see Table 2.

Table 2: Censoring Rules for DoCB, DoR and TTP

Situation	Date of Progression or Censoring	Outcome
Disease Progression	Date of progression	Progressed
No baseline tumor assessment	Date of first treatment	Censored
No disease progression	Date of last tumor assessment	Censored
Subject received non-study MM treatment before disease progression	Date of last tumor assessment prior to non-study treatment	Censored

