Death from other causes than disease progression, without documented disease progression before	Date of last tumor assessment	Censored
Death caused by disease progression between adequate assessments	Date of death	Progressed
Death caused by disease progression or progression after > 65 days (2x 29-day cycle +7 days) after last tumor response assessment (representing the time interval of 2 or more consecutive missed tumor response assessments)	Date of last tumor assessment	Censored

Progression-free survival (PFS): Progression-free survival will be defined as the time from

Cycle 1, Day 1 until date of progression (as defined above) or date of death, whatever occurs earlier, or date of censoring (as defined below). For censoring rules see Table 3.

Table 3: Censoring Rules for PFS

Situation	Date of Progression or Censoring	Outcome
Disease progression	Date of progression	Progressed
No post-baseline tumor assessment	Date of first treatment	Censored
No disease progression	Date of last tumor assessment	Censored
Subject received non-study MM treatment before disease progression	Date of last tumor assessment prior to non-study treatment	Censored
Death before any date of PD assessment	Date of death	Progressed
Death between adequate assessments	Date of death	Progressed
Death or progression after > 65 days (2x 29-day cycle +7 days) after last tumor response assessment (representing the time interval of 2 or more consecutive missed tumor assessments)	Date of last tumor assessment	Censored

Additional time to event variables:

Duration of clinical benefit (DoCB): The duration of clinical benefit will be calculated in the subgroup of subjects showing confirmed sCR, CR, VGPR, PR or MR. Duration of clinical benefit will be defined as the time from date of first clinical benefit (sCR, CR, VGPR, PR or MR) until date of progression or death due to progression (as defined above), whichever is documented first. For censoring rules see Table 2.

Additionally, the DoR of sCR/CR and sCR/CR/VGPR according to the above defined rules will be reported separately.

Time to next treatment (TTNT): TTNT will be defined as the time from Cycle 1, Day 1 until start date of new anti-MM treatment as documented at the end of trial visit under “Subsequent anti-MM Treatment” or date of death. Subjects with no documented start date for a subsequent anti-MM treatment and no documented date of death will be considered censored using the date of the last visit.

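### Start of new anti-myeloma treatment is a progression event in Protocol 11.1.1 but is censored in SAP Tables 2 and 3; one PFS row and the TTNT rule also need repair

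*Protocol*

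**What the plan says.** **Event definition.** Protocol 11.1.1, which names DoR, TTP and PFS as efficacy measures, reads: "Disease progression is defined as progressive disease according to the IMWG, 2006 (see Appendix 18.3, Table 14), death or start of new anti-MM treatment". SAP 7.3.3.3 has the same situation in Table 2 (DoCB, DoR, TTP) and Table 3 (PFS): "Subject received non-study MM treatment before disease progression". Both tables date it to "Date of last tumor assessment prior to non-study treatment" and give the outcome as censored.

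The two tables also censor late events, back to the last assessment. Table 2 has "Death caused by disease progression or progression after > 65 days" and Table 3 has "Death or progression after > 65 days (2x 29-day cycle +7 days) after last tumor response assessment". Table 2 further censors "Death from other causes than disease progression, without documented disease progression before".

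Elsewhere the protocol treats progression, new therapy and death as three separate things. Follow-up continues "until progressive disease, or receipt of new anti-myeloma treatment, or until death" (Table 1, footnote 1), and 10.1.12 has visits repeated "until there is a disease progression (but no longer than 3 years), death, or the subject starts a new anti-myeloma therapy".

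**Early deaths.** Row 2 of SAP Table 3 censors, at first treatment, a subject with no tumor assessment after baseline. Row 5 counts a death that precedes any PD assessment as an event on the date of death. No order of precedence is given.

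**TTNT.** SAP 7.3.3.3 adds time to next treatment, with start of new therapy or death as the event. Subjects with neither date documented are censored at the last visit. SAP 8.3 says the next therapy is recorded only for subjects included under amendment 6 or later. Protocol 10.1.14 intends the EOS visit to come before any new myeloma therapy.

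**The concern.** The SAP says it implements this same protocol version (12.0), yet the two documents can assign the same subject opposite event status on three secondary endpoints. Someone working from the protocol and someone working from the SAP would report different Kaplan-Meier estimates for PFS, TTP and DoR. SAP estimates would usually be the longer ones, because an event is turned into a censored time.

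The other two items are separate faults within the SAP. Two programmers could code an early death differently in the PFS table. And TTNT handles data that were never collected as if no next therapy had started. The number of subjects per part is small: Protocol 15.9 guarantees only 9 in each recommended-dose group. One reclassified subject can therefore be visible in the result.

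**Working it through.** **1. Event status side by side**

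| Situation | Protocol 11.1.1 | SAP Table 2 (DoCB, DoR, TTP) | SAP Table 3 (PFS) |
|---|---|---|---|
| IMWG PD | event | event | event |
| New treatment before PD | event | censored | censored |
| Death from another cause, no PD | event | censored | event |
| PD, or relevant death, more than 65 days after last assessment | event; no gap limit stated | censored | censored |

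The second row is the conflict. In the third row the protocol sentence is the one out of line: if every death is progression, TTP equals PFS, although the endpoint list in Protocol 11 names both. The fourth row is a rule the SAP adds where the protocol has no censoring rules. Its cut-off reproduces: 2 × 29 + 7 = 65 days. With the stated 28-day cycle it would be 2 × 28 + 7 = 63.

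**2. Size of the new-treatment difference.** The documents give no share of switches, so this is an assumed range. Let q be the share of first events under the protocol definition that are switches without PD. With constant competing hazards, censoring them leaves a fraction (1 − q) of the event hazard, so the median is multiplied by 1/(1 − q):

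- q = 0: 1.00
- q = 10%: 1/0.90 = 1.11
- q = 20%: 1/0.80 = 1.25
- q = 30%: 1/0.70 = 1.43

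In 20,000 simulated curves with n = 9, an assumed 5-month median and assessments every 28 days, the typical median of 5.0 months becomes 5.5, 6.2 and 7.0 at q = 10%, 20% and 30%. It is unchanged in 70%, 46% and 29% of curves. Under the same assumptions the sample median of 9 subjects itself ranges from about 1.7 to 11.2 months (95%), which is wider than any of these shifts.

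A hand example: 9 subjects, first events at months 1 to 9, with those at months 2 and 4 being switches.

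- Counted as events: the curve is 4/9 = 44% at month 5, so the median is 5. PFS at 6 months is 3/9 = 33%.
- Censored: 8/9 × 6/7 × 4/5 = 61% at month 5, then × 3/4 = 46% at month 6. The median is 6 and PFS at 6 months is 46%.

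**3. Death before any post-baseline assessment.** Take 9 subjects, one such death, and the other 8 event-free at 2 months. Under row 5, PFS at 2 months is 8/9 = 89%. Under row 2, it is 100%. The conflict cannot arise in the Efficacy Evaluable Population, because SAP section 6 requires a post-baseline investigator response assessment for entry. It can arise in the Safety Population, where SAP 9.2 also reports PFS.

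**4. TTNT.** Let u be the share of subjects without next-therapy capture. If their last visit falls just before the uncollected therapy start, nearly all of their events are lost, and the ratio to the true median tends to 1/(1 − u): 1.11, 1.33 and 2.00 for u = 10%, 25% and 50%. Large-sample Kaplan-Meier estimates were run over assumed PD medians of 3 to 8 months, next therapy 0.9 to 3 months after PD, and a last visit 0.03 to 2 months before it. The ratios were 1.04–1.10, 1.10–1.30 and 1.31–1.90. One cell (PD median 5, therapy 1.5 months after PD, last visit 0.58 months before therapy) has a true median of 6.5 months and estimates of 7.0, 8.0 and 11.1.

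**The case against.** The strongest case against starts from the protocol sentence itself. It collapses TTP into PFS and disagrees with the protocol's own follow-up rules, so it is a poor standard for judging the SAP, whose rules are written out in full. That stands, and it is why either document may be the one corrected.

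Switching before PD may also be rare. SAP 8.3 treats other myeloma therapy on study as non-compliance, and the withdrawal reason listed in Protocol 8.7.1 is treatment needed because of progression. This stands as a limit on size. SAP EFS does count new treatment as an event, and SAP 9.2 tabulates censoring reasons for PFS. But EFS pools switches with every other discontinuation, and the tabulation covers neither TTP nor DoR.

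On Table 3, one can argue that row 5 is naturally read as overriding row 2, since the PFS definition makes any death an event. That is plausible, but the table does not say so. On TTNT, the recommended-dose tables cover only Parts C to E (SAP 7.2), and the uncaptured subjects would be among the earliest enrolled, so the share there could be zero. The documents do not date amendment 6.

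A reader might infer more than the text allows:

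- *That the SAP concealed a departure.* Protocol 15.13 places the description of deviations in the clinical study report, and the SAP's front matter and section 11 text are not in the supplied copy.
- *That the 65-day rule contradicts the protocol.* Protocol 11.1.1 and 15.4 contain no censoring rules, so it is an explicit addition.
- *That censoring non-PD deaths in Table 2 is an SAP error.* It is what keeps TTP distinct from PFS.

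**Conclusion.** The mismatch is real: start of new treatment before PD is an event under Protocol 11.1.1 and censored under SAP Tables 2 and 3. The two-outcome problem in Table 3 holds for the Safety Population only. The TTNT bias holds wherever subjects without next-therapy capture are included.

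The size is unknown and could be nil. For new treatment, the ratio of medians runs from 1.00 to 1.43 over an assumed 0–30% share of switches. For TTNT, it runs from 1.04 to 1.90 over an assumed 10–50% uncaptured. Both ranges rest on assumed exponential or similar timing and on shares that the documents do not give. The direction is usually towards longer times under the SAP, but at n = 9 the median often does not move.

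A reader might also infer that the trial's main conclusions are at risk. They are not: no test, primary endpoint or MTD decision uses these variables. They are descriptive secondary endpoints (PFS, TTP, DoR) or additional SAP variables (DoCB, TTNT). The point should be put right, but it is not critical.

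**What to change.** - Reconcile Protocol 11.1.1 with SAP Tables 2 and 3 so that one event definition governs and TTP stays distinct from PFS. Correcting the protocol sentence is as acceptable as correcting the tables.
- Report, per part, the number of subjects whose PFS, TTP or DoR status differs between the two definitions. A full second set of Kaplan-Meier tables is not needed.
- Describe the 65-day rule as an SAP addition among the deviations that Protocol 15.13 requires in the study report.
- In Table 3, extend row 2 so that it applies only when there is no post-baseline tumor assessment and no death.
- Restrict TTNT to subjects with next-therapy capture and give the number excluded per part.

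The cost is some SAP wording or one protocol sentence, one small table, and a smaller N for TTNT. No new data are needed.

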## 11.1.2 Immune Cells

For evaluation of the status of the immune system, B, T, and NK cells will be measured frequently throughout the study. The absolute and percent changes from baseline will be evaluated.

Flow cytometry of peripheral MM cells and CD16 expression on NK cells will be evaluated at baseline and at Day 29 (Cycle 2 Day 1) (exploratory assay).

Pending sample availability, endogenous antibody titers (e.g., tetanus titers) will be measured from remaining anti-MOR03087 antibody back-up samples in order to gain information about the influence of MOR03087 treatment on normal plasma cells and immunity, especially when MOR03087 is administered over extended periods of time.

